15. DATA AND SAFETY MONITORING PLAN

A specific data and safety monitoring plan is only required for greater than minimal risk research. For guidance on creating this plan, please see the [Guidance Document](#) on the HRPP website.

Part I – this part should be completed for all studies that require a DSMP.

Part II – This part should be completed when your study needs a Data and Safety Monitoring Board or Committee (DSMB/C) as part of your Data and Safety Monitoring Plan.

Part I: Elements of the Data and Safety Monitoring Plan

- *Indicate who will perform the data and safety monitoring for this study.*
- *Justify your choice of monitor, in terms of assessed risk to the research subject's health and well being. In studies where the monitor is independent of the study staff, indicate the individual's credentials, relationship to the PI, and rationale for selection*
- *List the specific items that will be monitored for safety (e.g. adverse events, protocol compliance, etc)*
- *Indicate the frequency at which accumulated safety and data information (items listed in # above) will be reviewed by the monitor (s) or the DSMB/C.*
- *Where applicable, describe rules which will guide interruption or alteration of the study design.*
- *Where applicable, indicate dose selection procedures that will be used to minimize toxicity.*
- *Should a temporary or permanent suspension of your study occur, in addition to the IRB, indicate to whom will you report the occurrence.*

Part II: Data and Safety Monitoring Board or Committee

- *When appropriate, attach a description of the DSMB.*
- *Provide the number of members and area of professional expertise.*
- *Provide confirmation that the members of the board are all independent of the study.*

Attached please find the Charter document for the Personalized Trials Pilots DSMB. Personnel, roles, and areas of expertise are listed. All voting members of the DSMB are independent of the study.

16. WITHDRAWAL OF SUBJECTS

- *Describe anticipated circumstances under which subjects will be withdrawn from the research without their consent*
- *Describe procedures for orderly termination*
- *Describe procedures that will be followed when subjects withdraw from the research, including partial withdrawal from procedures with continued data collection.*

Circumstances under which participants may be withdrawn from the research without their consent include failure to maintain protocol adherence, ,self-reported

adverse side effects to two or more interventions, significant cell phone carrier issues that prevent the participant from receiving study text messages, it is not in the participant's best interest to continue in the pilot, and the pilot study is stopped. We will not withdraw a participant based on non-adherence to wearing their Fitbit, taking their supplement, or completing daily surveys, as this absence of data is useful for feasibility purposes. Because of this, lack of adherence to Fitbit wear, taking the supplements, or completion of daily surveys are not considered protocol deviations.

A potential participant will not be randomized to receive the intervention protocol until he/she has demonstrated at least 80% adherence to continuous Fitbit monitoring (activity recorded > 12 hours/day, and recorded sleep activity) and response to survey questionnaires during the baseline period.

Potential participants will be notified of the possibility of being removed from the study before intervention randomization due to adherence issues in the informed consent. Participants who fail to maintain minimum adherence during baseline will be notified by the research team in the first 10-14 days of baseline participation. These participants will stop receiving notifications and survey prompts and will receive instructions to un-link their Fitbit device. The participant will be able to keep their Fitbit.

Participants who fail to maintain protocol during the intervention period will be contacted by a member of the study team with a reminder of the study protocol and will be informed that this may impact their continued study eligibility. Once a protocol deviation has been repeated, the Principal Investigator will determine the participant's continued eligibility in the study, with consultation of the DSMB if needed. If it is determined that the participant will be withdrawn from the study, the participant will be notified of their withdrawal from the study by the research team via text message. The participant will stop receiving notifications and survey prompts and will be sent instructions to un-link their Fitbit device. The participant will be able to keep their Fitbit device. The participant will be asked to return their 3 Nomi pill bottles, the Nomi charger, and any unused pills to the study team, as they would at regular study end.

Should a participant choose to withdraw from research, they will be instructed to send a letter or e-mail to the attention of the Principal Investigator at our [name] office, or to email [contact], an e-mail account monitored by IRB-approved members of the research team. Participants will be contacted by a member of the research team confirming their study withdrawal, and to answer any questions the participant may have. The participant will stop receiving notification and survey prompts and will be sent instructions to un-link their Fitbit device. They will be able to keep their Fitbit device. Data collection will stop the business day the letter or e-mail is received. All data up until the receipt

date of the letter or e-mail will be included in the research study. The participant will be asked to return their 3 Nomi pill bottles, the Nomi charger, and any unused pills to the study team, as they would at regular study end.

Partial withdrawal, defined as study participation and data collection without the use of one of the melatonin/placebo supplements will be allowed if a participant experiences an adverse event to one of the intervention options (3mg dose melatonin, 0.5mg dose melatonin, or placebo). In instances where participants contact the research team to self-report serious side-effects or otherwise contact the research team with concerns about their self-reported side effects, participants will be permitted to continue their involvement in the study, should they be interested. Participant data will continue to be collected and monitored, while removing the self-reported adverse intervention option from their randomized protocol (i.e. skip the intervention days and continue with placebo and/or other intervention). This will allow the participant to still evaluate their individual response to the self-reported non-aggravating intervention option. In the event that both intervention options create self-reported adverse events for the participant, they will be withdrawn from the study.]

Participants who are deemed ineligible and removed from the study during the intervention period (but not the baseline period) and participants who are withdrawn from the study will still be asked to complete the end-of-study satisfaction survey and follow-up interview. These participants will not receive a personalized participant report, and therefore the questions asked in the satisfaction survey and follow-up interview will be abbreviated (will not include the approved questions about the participant report asked of other participants).

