8. NUMBER OF SUBJECTS

- *Indicate the total number of subjects to be accrued locally. If applicable, distinguish between the number of subjects who are expected to be pre-screened, enrolled (consent obtained), randomized and complete the research procedures.*
- *If your study includes different cohorts, include the total number of subjects in each cohort.*
- *If this is multisite study, include total number of subjects across all sites.*

Up to 500 potential participants will be invited to enroll. Up to 60 participants will be randomized to complete research procedures.

Of those participants who receive randomized intervention schedules, 30 participants will be randomized to receive the study protocol in the following order of two-week intervention periods: 3 mg Dose Melatonin, .5 mg Dose Melatonin, Placebo, Placebo, .5 mg Dose Melatonin, 3 mg Dose Melatonin (ABCCBA). The remaining 30 participants will be randomized to receive the study protocol in the following order of two-week intervention periods: Placebo, .5 mg Dose Melatonin, 3 mg Dose Melatonin, 3 mg Dose Melatonin, .5 mg Dose Melatonin, Placebo (CBAABC).

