During all intervention weeks (12 weeks total), participants will be asked to continue wearing their Fitbit device each day and night. They will continue to receive 3 randomized text message surveys each day with questions about their pain, fatigue, concentration, confidence, mood, and stress at that current moment, as well as a morning text asking them to report on their sleep quality the previous night, using a modified Consensus Sleep Diary. Morning surveys during the intervention weeks will also include questions about any melatonin or placebo-related side-effects the participant is experiencing. At the end of each intervention period on Sunday evening (every two weeks), participants will receive a slightly longer survey that includes the Insomnia Severity Index. A study phone number and email address will be available as part of each survey to contact the study team

if a participant is concerned about any side effects they are experiencing. Participants will be instructed to contact 911 or go to the nearest emergency room in the event of a medical emergency. In addition, participants will be advised to stop taking their pills if they are concerned about side effects.

Participants may receive additional text messages to those outlined above with important reminders about their protocol (e.g., transition to a new intervention period), or to remind participants to sync their data or charge their devices. We will send a maximum of 5 text message surveys per day during the study, as well as text messages of these reminders and other important study communications.

In the event of an unanticipated circumstance that temporarily prevents a participant from completing study activities (illness, injury, death in the family, etc.), the participant will have the option of pausing their study to resume once their circumstance has been positively resolved.

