As per the manufacturer's recommendations, individuals who are pregnant or lactating, or taking MAO inhibitors or corticosteroids will be screened out, as well as those with depression, seasonal affective disorder, schizophrenia, autoimmune disease, and asthma to avoid contraindications. Potential participants with these conditions will screen out of the study.

We will emphasize to subjects in the intervention arm that they can stop taking supplements or withdraw from the N-of-1 trial completely at any point, particularly if they experience any concerning side-effects. Participants will be instructed to contact 911 or go to the nearest emergency room in the event of a medical emergency. Additionally, the Principal Investigator will review any serious adverse events and these will be reported to the DSMB. All data concerning adverse outcomes will be reviewed by the DSMB at least once a year. Any serious adverse effects will also be reported to the IRB.

Surveys

Should a participant report emotional distress in responding to survey questions, the research coordinators will refer to our Principal Investigator (a licensed clinical psychologist), who will recommend follow-up.

Fitbit

There is no additional risk with using a Fitbit activity monitor for research as compared to using the device as a consumer, including mild skin irritation (i.e. contact dermatitis) which occurs among a small proportion of users. Participants will be instructed via the consent form on methods to reduce irritation (e.g. keep

the band clean and dry) and that they can remove the band for a short period of time.

Loss of Confidentiality or Privacy

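### In CBAABC, a participant who drops 0.5 mg melatonin in period 2 for an adverse event may go on to a first in-study 3 mg dose, blinded to dose, with no review required before that dose

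*Combined protocol and SAP*

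**What the plan says.** Section 8 (Number of Subjects) sets two orders of two-week periods, each for 30 participants: ABCCBA and CBAABC, where A is 3 mg melatonin, B is 0.5 mg and C is placebo. Section 11 supplies no melatonin at baseline, so all study exposure starts in period 1.

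Section 16 (Withdrawal of Subjects) allows partial withdrawal after an adverse event on one option. The option concerned is removed and the participant may "skip the intervention days and continue with placebo and/or other intervention". For participants who report serious or worrying side effects, the stated condition is: "participants will be permitted to continue their involvement in the study, should they be interested". The reason given is that the participant can still "evaluate their individual response to the self-reported non-aggravating intervention option". Full withdrawal is prescribed only at a later point: "In the event that both intervention options create self-reported adverse events for the participant, they will be withdrawn from the study".

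Section 12 (Statistical Analysis) keeps participants blinded to what each letter stands for until the summary report. Coordinators are not blinded.

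On review, Section 17 (Risks to Subjects) states that "the Principal Investigator will review any serious adverse events and these will be reported to the DSMB". It also sends serious events to the IRB and has the DSMB look at all adverse outcomes at least yearly. For repeated protocol deviations, Section 16 has the Principal Investigator decide on the participant's "continued eligibility in the study, with consultation of the DSMB if needed". No such decision is stated for adverse events.

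**The concern.** The partial-withdrawal rule treats the three options as interchangeable: drop the one that caused trouble and carry on with the rest. But two of them are the same substance at different doses. Dropping the higher dose and keeping the lower one is a cautious step. Dropping the lower dose and then starting the higher one for the first time is an escalation after an event, and the rule does not tell the two apart.

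The only stated condition for continuing is the participant's interest, yet the participant does not know that the event came on the lower dose or that the next bottle holds the higher one. The coordinators do know, but no step tells them to act on it.

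What is at stake is the safety of a few participants. Among the less common effects, Section 17 lists low mood, confusion and low blood pressure, while Section 7 (Eligibility Criteria) excludes people diagnosed with depression or low blood pressure. Someone who reports such an effect on 0.5 mg could start 3 mg without a recorded decision that this is acceptable.

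**Working it through.** The plan gives no figure to reproduce. The check is to run the Section 16 rule through the Section 8 schedules.

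| Sequence | P1 | P2 | P3 | P4 | P5 | P6 |
|---|---|---|---|---|---|---|
| ABCCBA | 3 mg | 0.5 mg | placebo | placebo | 0.5 mg | 3 mg |
| CBAABC | placebo | 0.5 mg | 3 mg | 3 mg | 0.5 mg | placebo |

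**Step 1: which 0.5 mg periods can lead to a first 3 mg exposure?** There are four.

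- ABCCBA, periods 2 and 5: 3 mg was taken in period 1. Had it also caused a reported event, the participant would be withdrawn because both doses had done so. Anyone who continues has already had 3 mg without a reported event, so this is not a first exposure.
- CBAABC, period 5: 3 mg was taken in periods 3 and 4, and none remains.
- CBAABC, period 2: only placebo and 0.5 mg have been taken, and 3 mg is next. This is a first in-study exposure.

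Result: 1 of 4.

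**Step 2: size of the step.** With 0.5 mg removed in period 2, CBAABC becomes placebo, stopped, 3 mg, 3 mg, skipped, placebo.

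- Dose ratio: 3 / 0.5 = 6.
- Scheduled 3 mg nights that follow: 2 × 14 = 28, out of 6 × 14 = 84 intervention nights (28 / 84 = 33%). This is the normal planned 3 mg exposure, not an excess.
- Gap before the first 3 mg night: for an event on night k of period 2, 14 − k nights, that is 13 down to 0 for k = 1 to 14. This assumes that skipped days stay on the calendar and that the event is reported the same night; Section 16 states neither.
- Share of participants in this sequence: 30 / 60. No event rate is given, so the number affected cannot be estimated.

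**Step 3: does any other provision have to be completed before that dose?**

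| Provision | Section | Why it does not hold the dose |
|---|---|---|
| Principal Investigator review of serious adverse events | 17 | No timing relative to the next period; non-serious events not covered |
| DSMB review of all adverse outcomes | 17 | At least yearly, against 12 weeks of intervention |
| Daily side-effect questions; advice to stop pills if concerned | 11 | Stopping is left to the blinded participant |
| Pausing: "the participant will have the option of pausing their study to resume once their circumstance has been positively resolved" | 11 | The participant's option |
| Voluntary withdrawal | 16, 17 | The participant's option |
| Withdrawal by the team, for best interest or side effects on two or more interventions | 16 | Permissive; no assessment required |

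None is a condition for starting period 3.

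**The case against.** The step is less bare than the partial-withdrawal paragraph suggests. Section 11 advises participants to stop their pills, not just one bottle, if side effects worry them, so going on is a positive choice. Partial withdrawal involves contact with staff who know the allocation and who, under Section 5, can reach the Principal Investigator daily. Someone with side effects on both placebo and 0.5 mg can already be withdrawn before 3 mg. The rule permits 3 mg but does not force it, since continuing on placebo alone is allowed.

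The harm is also inferred. Section 17 describes mild side effects with a low chance of occurring. Section 3 puts 3 mg within the commonly used range and mentions over-the-counter doses up to 10 mg. Section 7 lets current melatonin users enrol, so for some people 3 mg is new only within the study.

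Finally, the phrase about a non-aggravating option may mean only an option not reported as aggravating, in which case the stated rationale is loose rather than wrong.

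All of this stands as a limit on the seriousness of the point. It does not close the gap: these safeguards rest on discretion or on a blinded participant. Under either reading of the phrase, 3 mg has not been tried in the study when the choice is made.

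**Conclusion.** The point holds as a minor patient-safety gap. In one period of one sequence, following Section 16 exactly can take a blinded participant from an adverse event on 0.5 mg to a first in-study dose six times as large, on interest alone. The required review of serious events has no timing relative to that dose, and non-serious events need no individual review.

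A reader might infer more than the documents support:

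- That adverse events go unreviewed. They do not: Section 17 requires Principal Investigator review of serious events, with DSMB and IRB reporting.
- That 3 mg has been shown to carry more risk. No rate by dose is given, so this is an inference.
- That 30 participants are exposed to the problem. That is the number planned for the sequence; those affected are the ones who drop 0.5 mg in period 2 and continue.
- That no rule exists anywhere. The consent form and the DSMB charter mentioned in Section 15 were not supplied. If either contains such a rule, Section 16 needs only a cross-reference.

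The primary System Usability Scale endpoint is unaffected.

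**What to change.** Add to the partial-withdrawal paragraph of Section 16:

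> If 0.5 mg melatonin is removed because of an adverse event before the participant has had any 3 mg period, 3 mg is also skipped and the participant may continue with placebo, unless before the first 3 mg dose the Principal Investigator, in consultation with a medically qualified DSMB member, records that the event has resolved and that 3 mg may be given.

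Medical input is needed because Section 17 describes the Principal Investigator as a licensed clinical psychologist. This assumes that the DSMB has a medically qualified member; if not, another medical reviewer should be named.

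Give every participant who partially withdraws, in either sequence, the same neutral message: remaining bottles may contain the same substance at a higher or lower dose, and continuing is optional. A message used only in CBAABC period 2 would hint at the dose, and Section 4 makes attitudes to the single-blinded placebo design a study goal. The rule for all other cases can stay as it is.

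Cost: a short protocol amendment, a coordinator script and a notice to the DSMB, with no extra participants. A participant who is not cleared loses 28 nights of 3 mg data and has no active option left to evaluate, but keeps 14 placebo nights from period 1 and 14 in period 6. If clearance is given and the skipped days stay on the calendar, a review of d nights delays 3 mg by max(0, d − (14 − k)) nights for an event on night k, at most d. For d assumed between 1 and 7, that is at most 1 / 28 = 4% to 7 / 28 = 25% of the 3 mg nights.

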17. RISKS TO SUBJECTS

- *Describe any potential risks and discomforts to the subject (physical, psychological, social, legal, or other) and assess their likelihood and seriousness and whether side effects are reversible. Where appropriate, describe alternative treatments and procedures that might be advantageous to the subjects.*
- *Include risks to others , like sexual partners (if appropriate)*
- *Discuss why the risks to subjects are reasonable in relation to the anticipated benefits and in relation to the importance of the knowledge that may reasonably be expected to results*
- *Describe the procedures for protecting against or minimizing any potential risks, including risks to confidentiality, and assess their likely effectiveness.*

This study poses no greater than minimal risk to subjects. Monitoring for adverse side-effects will be performed during the N-of-1 trial. Subjects will be encouraged to adhere to the supplement protocol, but will also be told that they can discontinue intervention at any time.

Melatonin was selected for this study as a minimal-risk sleep quality intervention option that has been shown to be a safe and effective option for many people. Some people, however, may experience mild side effects from melatonin. The most common side effects are headache, dizziness, nausea and sleepiness²¹. Less common side effects include short-lasting feelings of depression, mild tremor, mild anxiety, abdominal cramps, irritability, reduced alertness, confusion or disorientation, and abnormally low blood pressure. There is a chance that participants could experience these side effects, however the chances are low given the duration and dosing proposed for this research^{24, 25}. Participants will be advised to neither drive nor operate heavy machinery within 5 hours of taking their nightly supplement. Participants will only be advised to take melatonin one hour before their bedtime. Study participants document side effects daily and may withdraw from the study at any time without consequence should these side effects be viewed as bothersome.

There is also the potential risk of loss of privacy of information pertaining to research material collected by the study. Yet, we will take precautions, described below, to minimize these risks.

Melatonin Adverse Events

As per the manufacturer's recommendations, individuals who are pregnant or lactating, or taking MAO inhibitors or corticosteroids will be screened out, as well as those with depression, seasonal affective disorder, schizophrenia, autoimmune disease, and asthma to avoid contraindications. Potential participants with these conditions will screen out of the study.

We will emphasize to subjects in the intervention arm that they can stop taking supplements or withdraw from the N-of-1 trial completely at any point, particularly if they experience any concerning side-effects. Participants will be instructed to contact 911 or go to the nearest emergency room in the event of a medical emergency. Additionally, the Principal Investigator will review any serious adverse events and these will be reported to the DSMB. All data concerning adverse outcomes will be reviewed by the DSMB at least once a year. Any serious adverse effects will also be reported to the IRB.

Surveys

Should a participant report emotional distress in responding to survey questions, the research coordinators will refer to our Principal Investigator (a licensed clinical psychologist), who will recommend follow-up.

Fitbit

There is no additional risk with using a Fitbit activity monitor for research as compared to using the device as a consumer, including mild skin irritation (i.e. contact dermatitis) which occurs among a small proportion of users. Participants will be instructed via the consent form on methods to reduce irritation (e.g. keep

the band clean and dry) and that they can remove the band for a short period of time.

Loss of Confidentiality or Privacy

All subjects will be informed that their responses are confidential and that they may refuse to participate in the project or withdraw at any time without explanation, and that such action will not affect their future interactions with their health care providers, employment, educational studies, or the research study. The risk of loss of confidentiality will be minimized by securely storing data including PHI in a Northwell-approved database and minimizing the use of PHI. To ensure confidentiality, all data containing personal identifiers, and used to track contact with patients, will be kept in a secure, password-protected, encrypted Northwell-approved database. No paper documents with personal identifiers will be kept. The PI will be responsible for ensuring that the confidentiality of the data is maintained at all times. All data will be obtained specifically for research purposes.

Personal or identifiable information is not stored on any of the devices used in this study. No information about the participants or the participants' health history will be shared with Nomi or Fitbit, except for the information the participants directly share themselves should they choose to use the device for personal use at the conclusion of the study. There is no additional risk with using Nomi or Fitbit as part of this research study as compared to using the device as a consumer.

